9.9.5 Sensitivity Analyses Using Alternative Event Definitions

As sensitivity analyses for the primary biomarker and primary efficacy analyses, analogous analyses as described in Sections 9.9.3.1 and 9.9.3.2 will be done using the following revised definitions related to an event of MCI due to AD:

- Revised Event Time Definition: For purposes of analysis, the revised **event time** of a CIAC confirmed event of MCI due to AD is the time from either:
 - (1) the randomization date to the **date of the first unscheduled comprehensive medical follow-up visit** which was triggered by the first of the two consecutive scheduled visits at which a subject was assessed with a diagnosis of MCI due to AD (or AD itself) by the CIAC; or
 - (2) the randomization date to the **date of the unscheduled comprehensive medical follow-up visit** which was triggered by the subject's last scheduled visit during the study because the subject was assessed (for the first and only time) with a diagnosis of MCI due to AD (or AD itself) by the CIAC.

The revised event time definition above changes the event time so that it is based on the date of the first unscheduled visit date at which a case of MCI due to AD was determined by CIAC (since CDR data isn't collected at scheduled visits).

9.9.6 Analysis of Key Secondary Variables

The change from baseline in cognitive battery composite score will be analyzed as a continuous variable by study visit using MMRM (mixed model for repeated measures) analysis of covariance with treatment, gender, center, visit, and treatment-by-visit interaction as fixed, categorical effects and education, age, baseline composite score, and baseline composite score-by-visit as continuous, fixed covariates. The effect at each time point for each treatment is allowed to vary freely, and an unstructured covariance matrix will be used to model the within-subject errors. The Kenward-Roger approximation will be used to estimate denominator degrees of freedom. Based on a Missing at Random (MAR), this analysis will be performed using observed case data only.

The SAS code for the MMRM analysis will be as follows:

```
Proc mixed data=all;
```

- class visit treat center gender subject;
- model Change = Baseline Baseline*visit treat center gender education age visit visit*treat /solution ddfm=KenwardRoger;
- repeated visit/subject=subject type=UN;
- lsmeans visit*treat / cl pdiff.

In the above model, Baseline is the baseline value and Change is the change from baseline value.

Similarly, the change from baseline in ADCS ADL-PI ADL total score will be analyzed as a continuous variable by study visit using MMRM, where the ADCS ADL-PI ADL total score Baseline, gender, education, and age will be used as the covariate adjustments in the MMRM.

Key secondary endpoints will be analyzed (including reporting mean differences, CIs, and p-values) using the FAS subjects in the primary efficacy population (high-risk, non-Hispanic/Latino subjects) using a 0.01 significance level.

Although change-from-baseline endpoints will be assessed at all visits, the primary time frame for purposes of efficacy analysis is the change from baseline to Month 48 (Year 4).

Missing data from this study will be reviewed carefully to evaluate any patterns in this study. Also, as a sensitivity analysis, pattern mixture models using standard SAS STAT procedures will be performed for the key secondary endpoints to address the possibility of missing data not at random. This method uses sequential regression and multiple imputation methodology to impute missing values after subjects' discontinuation from the study. The missing values from both control and experimental treatment arms will be imputed based on the available data from control subjects and using PROC MI methodology for imputation of monotone missing data

patterns to impute the outcome variables at consecutive visits in a sequential (chain) manner. The number of imputed datasets will be 100.

Alternative methods of analysis (eg, using a transformation of the response variable or by using generalized estimating equations in SAS PROC GLIMMIX or PROC GENMOD) may be considered prior to unblinding should some of the underlying model assumptions (eg, normality) seem severely violated. The reasons for any changes to the planned approach and methods will be fully documented.

9.9.7 Derivation of Cognitive Battery Composite Score

The cognitive test battery by domain is described in [Appendix D](#). To form the composite score, z-scores will be calculated for each test listed below.

Episodic Memory domain	CVLT-II Short-delay free recall correct CVLT-II Long-delay free recall correct BVM-T-R Delayed Recall
Executive Function domain	Trail Making (Part B) – Total Seconds WAIS-III Digit Span – Backward
Language domain	Semantic fluency (animals) Lexical/phonemic fluency (letters “F-A-S”)
Attention	WAIS-III Digit Span – Forward Trail Making Test (Part A) – Total Seconds

The z-scores for measures in each domain will be averaged to create the four domain scores, and all four domain scores will be averaged to form the cognitive battery composite score. Because there are two tests for each domain, the domain score can still be calculated if one test is missing. One exception is the case of memory domain, where at least one subtest from the CVLT-II episodic memory tests is required to calculate the composite (i.e., CVLT-II Short-delay free recall correct or CVLT-II Long-delay free recall correct must be non-missing). For the calculation of the memory domain score, the following 3 measures are used (and given equal weight): CVLT-II Short-delay free recall correct, CVLT-II Long-delay free recall correct, and BVM-T-R Delayed Recall. If any of the domain scores is missing, then the composite score is set to missing.

For any visit, the z-score for a measure is calculated by taking the value for the measure at that visit, subtracting off the baseline mean for that measure, and then dividing by the baseline standard deviation for that measure. The baseline mean and baseline standard deviation for a measure will be calculated using all of the non-missing baseline values for subjects in the primary efficacy analysis population of high-risk, non-Hispanic/Latino Caucasian subjects.

The z-scores will only be used for the analyses and summaries of endpoints which are derived using multiple components (eg, the composite score and domain scores). All other endpoints will be analyzed and summarized using raw scores.

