Composite scores will be derived from the test battery. Each test in the battery falls into one of the following cognitive domains: Episodic Memory (CVLT-II, BVMT-R), Executive Function (TMT Part B, Digit Span Backwards), Language (Animals, Lexical/Phonemic Fluency), Attention (Digit Span Forward, TMT Part A), and Visuospatial (CDT, BVMT-Copy). Only the domains of episodic memory, executive function, language, and attention will be used for the composite score (ie, CDT, BVMT-Copy and the MINT, which do not allow generation of standard z scores, will only be used for diagnostic purposes and will be excluded from the calculation of the composite score). To form the composite, z-scores will be calculated for each

CONFIDENTIAL

test, each z-score for the domain will be averaged, and then all relevant domains will be averaged to form the composite. Because there are two tests for each domain, the composite can still be calculated if one test is missing. In the case of memory however, both tests are required to calculate the composite.

There may still be missing values for the continuous variables and the analyses for continuous variables are based on a Missing at Random (MAR) assumption. As a sensible sensitivity analysis, the pattern mixture models using standard SAS STAT procedures will be performed. This method uses sequential regression and multiple imputation methodology to impute missing values after subjects' discontinuation from the study. The missing values from both control and experimental treatment arms are imputed based on the available data from control subjects and through using PROC MI's methodology for imputation of monotone missing data patterns to impute the outcome variables at consecutive visits in a sequential (chain) manner.

Additional analyses may be done to assess the contribution of age, APOE genotype, and TOMM40 rs10524523 genotype to the risk assignment algorithm.

It is anticipated that approximately 20% of the subjects will be diabetic. Subgroup analyses for non-diabetic subjects and for diabetic subjects will be done to support the results of the primary analysis.

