9.1.2 Summary Statistics and Precision

All tabulations of analysis results will include summaries for all three treatment groups: high-risk placebo, high-risk pioglitazone, and low-risk placebo.

Except when noted as otherwise, all confidence intervals (CIs), statistical tests, and resulting p-values will be reported as nominal 2-sided and will be assessed at the 5% significance level. No adjustments will be made for multiplicity except for primary efficacy and key secondary endpoints.

For continuous variables, descriptive statistics will include the number of subjects (n), mean, standard deviation (SD) or standard error (SE) as appropriate, minimum, median, and maximum. The number of decimal places displayed for each statistic will be determined as follows:

- Mean and median: 1 more than the number of reported decimal places. (For electronic case report form (eCRF) data, the number of reported decimal places will be equal to the number of decimal places allotted in the eCRF.)
- SD and SE: 2 more than the number of reported decimal places allotted in the eCRF.
- Minimum and maximum: equal to the number of reported decimal places allotted in the eCRF.
- Confidence intervals will be presented using the same number of reported decimal places as the parameters (eg, mean).

For categorical data, frequency counts and percentages will be presented. Percentages will be reported to 1 decimal place.

The data summaries will be accompanied by individual subject data listings sorted by treatment (including low-risk placebo), study center and subject identifier. All data available from eCRFs will be listed. The actual day relative to the start of treatment will be determined and included in the listings.

Derived analysis datasets will be produced from SDTM data and laboratory data. This allows for convenient reviewing of the data as well as any necessary supplemental analyses. All data from the raw datasets will be included in the derived datasets. Derived dataset specifications will be developed to include the names and definitions of derived variables in the derived SAS datasets.

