9.9.1 Overview of Primary, Secondary, and Additional Variables

The primary, secondary and additional variables for this study are presented in [Table 9.b](#). While most of the variables in the table are technically discrete, the variable type column indicates how the variables will be considered for purposes of analysis.

Table 9.b Primary, Secondary and Additional Variables

Parameter	Description	Range	Variable Type
MCI_TIME	Time to event of MCI due to AD	N/A	Time-to-event
MMSE	Total of all items correct	0-32	Continuous
MMSE _i	MMSE single item i	0-5	Categorical
BVMT_T1	# of elements recalled, Trial 1 (0-12 possible)	0-12	Continuous
BVMT_T2	# of elements recalled, Trial 2 (0-12 possible)	0-12	Continuous
BVMT_T3	# of elements recalled, Trial 3 (0-12 possible)	0-12	Continuous
BVMT_TOT	Total # of elements recalled, Trials 1-3	0-36	Continuous
BVMT_DEL	Total # of elements recalled after a delay (25-minute delay)	0-12	Continuous
BVMT_HIT	Total # of target elements correctly recognized	0-6	Continuous
BVMT_FP	Total # of foils incorrectly endorsed	0-6	Continuous
BVMTDISC	Total target elements correctly recognized relative to Total false positives	-6 to 6	Continuous
BVMTCOPY	Total # of elements copied correctly	0-12	Continuous
DIGIT_F	Total items correct, Digit Span Forward	0-16	Continuous
DIGIT_B	Total items correct, Digit Span Backward	0-14	Continuous
DIGITOT	Total Forward + Back	0-30	Continuous
TRAILSAS	# of seconds to complete all items, Trails A	0-300	Continuous
TRILSAE	Errors (number of errors committed during the test)	0-5	Continuous
TRAILSBS	# of seconds to complete all items, Trails B	0-300	Continuous
TRILSBE	Errors (number of errors committed during the test)	0-15	Continuous
MINT	Total correct, MiNT	0-32	Continuous
SEMFLU	Number of exemplars generated in 1 minute (up to max=100)	0-100	Continuous
LEXFLU	Number of exemplars generated total for F, A, and S (up to max 267)	0-267	Continuous
LEX_F	Number of exemplars generated in 1 minute (up to max=89)	0-89	Continuous
LEX_A	Number of exemplars generated in 1 minute (up to max=89)	0-89	Continuous
LEX_S	Number of exemplars generated in 1 minute (up to max=89)	0-89	Continuous
CLOCK	Number of elements correct (eg, clock face, hands, number placement), Clock Drawing Test	0-10	Continuous
CVLT_T1	# of words (out of 16), recalled 1st trial	0-16	Continuous
CVLT_T2	# of words (out of 16), recalled 2nd trial	0-16	Continuous
CVLT_T3	# of words (out of 16), recalled 3rd trial	0-16	Continuous

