 - Fails at least one of the two memory tests in the cognitive test battery (failure defined as an individual test score at or below -1.5 SD of the demographically corrected normative mean (a), and the score reflects a change from baseline).
 - Fails 2 or more of the 12 measures in the cognitive test battery, representing separate cognitive domains.
 - (Failure is defined as an individual test score at or below -1.3 SD (10th percentile) of the demographically corrected normative mean, and the score reflects a change from baseline).

Examine etiology of MCI consistent with AD pathophysiological process

- Rule out vascular, traumatic, psychiatric, and other proximal medical causes of cognitive decline.
- Continued evidence of cognitive impairment or continued decline on 6 month follow-up (ie, 2 consecutive study visits showing impairment). (b)

(a) Normative data will be available per language.

(b) It is not required that the two consecutive visits show an identical profile (ie, meeting any definition of MCI due to AD on two consecutive visits is acceptable for a subject to be forwarded for adjudication). Note that the two consecutive visits must contain non-missing determinations of MCI due to AD status in order to contribute to the determination of an adjudicated event of MCI due to AD.

The criteria for triggering possible cases for adjudication are provided in the appendix of the CIAC Charter. For purposes of triggering possible cases, the choice of tests to assess the cognitive domains differs slightly from the table in [Appendix D](#). In particular, the Executive Function domain is assessed using Trail Making Test Part B and digit span total (rather than digit span backwards). And the attention domain consists only of Trail Making Test Part A (and does not include digit span forward).

The CVLT-II memory test consists of 3 measures, two of which are important for purposes of triggering and for calculation of the composite score: Short-Delay Free Recall and Long-Delay Free Recall. Of those two CVLT-II measures, only Long-Delay Free Recall is used for inclusion/exclusion. For post-baseline visits, failure on either of the two measures indicates failure on the CVLT-II test.

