9.9.8 Controlling Type I Error

To control the two-sided type I error over all the efficacy endpoints that are intended to support potential claims, the primary and key efficacy endpoints will be tested in the following sequential order at significance level 0.01; as soon as an efficacy endpoint test is non-significant at $\alpha=0.01$, the testing procedure stops for all subsequent endpoints:

- Time to diagnosis of MCI due to AD for pioglitazone-treated, non-Hispanic/Latino Caucasian subjects versus placebo-treated non-Hispanic/Latino, Caucasian subjects in the high-risk stratum.
- Change from baseline to Year 4 for cognitive decline on composite score on the cognitive battery for pioglitazone-treated, non-Hispanic/Latino Caucasian subjects versus placebo-treated non-Hispanic/Latino, Caucasian subjects in the high-risk stratum.
- Changes from baseline to Year 4 in instrumental activities of daily living (Alzheimer's Disease Cooperative Study Activities of Daily Living - Prevention Instrument [ADCS-ADL-PI]) for pioglitazone-treated, non-Hispanic/Latino Caucasian subjects versus placebo-treated non-Hispanic/Latino, Caucasian subjects in the high-risk stratum.

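### The composite score averages Trail Making seconds, where higher is worse, with tests where higher is better, and no sign is reversed

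*SAP*

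**What the plan says.** SAP 9.9.7 builds the composite from nine measures in four domains. The two timed tests, Trail Making B (executive function) and Trail Making A (attention), are entered as total seconds. Each is paired with a Digit Span count.

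One rule applies to every measure: "the z-score for a measure is calculated by taking the value for the measure at that visit, subtracting off the baseline mean", with the result divided by the baseline SD. The mean and SD come from the study's own high-risk, non-Hispanic/Latino Caucasian baseline values. After that, "The z-scores for measures in each domain will be averaged to create the four domain scores", and the four domains are averaged with equal weight. Outside memory, "the domain score can still be calculated if one test is missing".

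SAP Table 9.b defines the Trails B variable as the number "of seconds to complete all items, Trails B", range 0 to 300, and defines Trails A in the same way. It defines the Digit Span, fluency, CVLT-II and BVMT-R components as numbers correct, recalled or generated.

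Protocol 13.1.3 describes the same construction ("To form the composite, z-scores will be calculated for each" test, then averages) and is also silent on direction. SAP Appendix D and the amendment text on 9.9.7 add nothing on the point.

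**The concern.** An average of z-scores has a meaning only if every component points the same way. Here seven components rise with better performance and two rise with worse performance. A drug that prevented slowing on Trails would look harmful on that part of the score.

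The composite is second in the fixed sequence of SAP 9.9.8, at a two-sided level of 0.01. Testing stops "as soon as an efficacy endpoint test is non-significant", so a failure on the composite also removes the ADCS ADL-PI test. The same scores are used in:

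- the MMRM of SAP 9.9.6, both as outcome and as baseline covariate;
- the domain analyses of 9.9.9;
- the high-risk versus low-risk placebo comparison of 9.9.10;
- the composite analyses given to the DSMB when conditional power is 30% or less (9.16). According to SAP 4.0, a nominally significant composite effect there decides whether the joint model is fitted.

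The one-test-missing rule adds a second problem. The direction of a subject's executive or attention score can depend on which of its two tests is missing.

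**Working it through.** The plan gives no power or worked example for the composite, so there is no stated figure to reproduce. The check applies the 9.9.7 rule as written, then again with the two Trails z-scores multiplied by -1.

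**Weights (SAP 9.9.7).** Memory has three measures: 1/3 x 1/4 = 1/12 each. Each of the other six measures has 1/2 x 1/4 = 1/8. Sum: 3/12 + 6/8 = 1.00. Trails A and B together: 0.25. The net weight with Trails unreversed is 0.75 - 0.25 = 0.50.

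**Direction, with no assumption beyond the SAP.**

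| Change | Executive | Attention | Composite as written | Composite with Trails reversed |
|---|---|---|---|---|
| Trails B 1 SD slower | +0.50 | 0 | +0.125 | -0.125 |
| Trails A and B 1 SD slower | +0.50 | +0.50 | +0.25 | -0.25 |
| All nine measures 1 SD worse | 0 | 0 | (-1 + 0 - 1 + 0)/4 = -0.50 | -1.00 |

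The executive and attention columns show the score as written.

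**Missing tests, all nine measures 1 SD worse.** The correct composite is -1.00 in each case.

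- Both executive tests present: executive 0, composite -0.50.
- Digit Span backward missing: executive +1, composite (-1 + 1 - 1 + 0)/4 = -0.25.
- Trails B missing: executive -1, composite (-1 - 1 - 1 + 0)/4 = -0.75.

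**Share of a raw group difference kept (assumed patterns).** Let Trails change k times as much, in SD units, as the other seven measures. The share is (0.75 - 0.25k)/(0.75 + 0.25k):

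- k = 0.5: 0.625/0.875 = 71%
- k = 1: 0.50/1.00 = 50%
- k = 1.5: 0.375/1.125 = 33%
- k = 2: 0.25/1.25 = 20%
- k = 3: 0%

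If memory changes m times as much as everything else, the share is (0.25m + 0.25)/(0.25m + 0.75). This is 60% at m = 2 and 67% at m = 3. If only memory changes, nothing is lost.

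**Standardised effect (assumed common correlation rho between measures, all scored so that higher is better).** The sum of squared weights is 3/144 + 6/64 = 0.1146. The variance of the correct composite is 0.1146(1 - rho) + rho. As written it is 0.1146(1 - rho) + 0.25 rho, because the net weight is 0.50. At rho = 0.2 the SDs are 0.540 and 0.376, so at k = 1 the ratio of standardised effects is 0.50 x 0.540/0.376 = 0.72. The other cases follow in the same way:

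| Pattern | rho 0.2 | rho 0.4 | rho 0.5 |
|---|---|---|---|
| k = 0.5 | 1.02 | 1.19 | 1.25 |
| k = 1 | 0.72 | 0.83 | 0.87 |
| k = 2 | 0.29 | 0.33 | 0.35 |
| Memory x2 | 0.86 | 1.00 | 1.05 |
| Memory x3 | 0.96 | 1.11 | 1.17 |

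Ratios above 1 arise because the unreversed terms also shrink the SD. At rho = 0 the SDs are equal, and the ratio is simply the raw share.

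**Power illustration, k = 1.** Suppose the correct composite had 90% power at two-sided 0.01. Power as written is Phi[(2.576 + 1.282) x ratio - 2.576]: 26% at rho 0 (ratio 0.500), 67% at 0.3 (0.783), 79% at 0.5 (0.874) and 85% at 0.7 (0.936).

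**The case against.** The strongest reply is that this is an omission in the wording and not evidence of a wrong analysis. SAP 9.1.2 says "Derived dataset specifications will be developed to include the names and definitions of derived variables", and those specifications, which are not among the documents, may contain the reversal. That is possible. But 9.9.7 cites no such specification, and protocol 13.1 makes the SAP the place for variable definitions. Section 9.9.7 also gives an explicit formula, which a literal programmer would follow. A programmer who reversed the sign would be departing from the written plan.

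A second reply is that the intended direction is obvious from the event criteria in SAP 9.9.4: "Failure is defined as an individual test score at or below -1.3 SD (10th percentile) of the demographically corrected normative mean". For a timed test this works only if low means worse. That shows intent but does not repair the rule. The event criteria use demographically corrected norms, whereas 9.9.7 standardises raw values on the study baseline.

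Third, the reach is limited, and this stands. The primary endpoint, event triggering and primary conditional power do not use the composite. The composite is formally tested only if the primary endpoint succeeds. With no effect on any component, the test keeps its type I error. Trails times are also analysed separately in seconds, which would show the conflict in direction. The futility rule is non-binding.

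Fourth, k, m and rho are all assumed. This also stands. Memory-led decline is plausible here, since both cognitive criteria in protocol Table 4.b require a memory failure, and in the memory-led rows above the standardised effect changes little. The documents give no missingness rates, so the practical weight of the missing-test problem is unknown.

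**Conclusion.** The concern holds for the rule as written. SAP 9.9.7 gives a quarter of the composite's weight the wrong sign: a 1 SD slowing on both Trails parts moves the score by +0.25 where it should move it by -0.25. This needs no assumption beyond the SAP's own weights and the fact that more seconds is worse.

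How much of a treatment difference would be lost is not determined by the documents. Under the assumed patterns the raw share kept runs from 0% to 100%. The standardised effect runs from about 0.29 to 1.25 of the correct one for correlations of 0.2 to 0.5 in the patterns tabulated, so power could fall or rise. A score that rewards slowing is not a valid measure of cognition in either case.

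Confidence is high that the reversal is absent from the protocol and SAP. What will actually be programmed cannot be known from them. Because the endpoint is alpha-controlled and meant to support a claim, the text must be corrected before unblinding.

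**What to change.** Add one sentence to SAP 9.9.7: *z-scores for Trail Making A and B total seconds are multiplied by -1 before averaging, so that higher is better for every component.* State that it applies wherever the composite, executive or attention score is used (9.9.6, 9.9.9, 9.9.10 and 9.16), and mirror it in protocol 13.1.3. If the derived dataset specification already reverses the sign, cite it in 9.9.7. With the reversal, a uniform 1 SD decline gives -1.00 in every domain and in the composite, whichever test is missing.

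The separate analyses of Trails in raw seconds need no change. The cost is one sentence and one line of code, with no new data. Made after unblinding, the same correction would look like a results-driven change to a confirmatory endpoint.
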